In Part 3, G100 Expansion of 20 μ g Dose Group, up to 25 patients will be enrolled and treated with intratumoral G100 at 20 μ g/dose following radiation therapy. The purpose of this group would be to explore the safety and potential clinical responses at the higher dose level. The number of patients was chosen to provide a similar cohort treated with G100 alone in Parts 1 and 2 for descriptive comparison. In those portions of the study, 18 patients (3 at 5 μ g/dose; 15 at 10 μ g/dose) may receive intratumoral G100 alone following radiation therapy.

In Part 4, G100 Plus Pembrolizumab, at least 22 evaluable patients will be enrolled and treated as part of a Dose Escalation group or a Patient Expansion group with intratumoral G100 in combination with pembrolizumab. The purpose of this treatment regimen will be to explore the safety and preliminary clinical efficacy and biomarker changes of patients treated with G100 at a dose of 20 μ g/lesion injected in single or multiple lesions. The administered dose of G100 will depend on the number of potentially injectable lesions and whether the MTD has been established during Dose Escalation. One or more lesions will be targeted for injection and each lesion would receive 20 μ g of G100 intratumorally (or 10 μ g G100 if 20 μ g/lesion in a single lesion is not tolerated) as long as the total number of treated tumor lesions and total systemic dose does not exceed the MTD (if established) or 80 μ g total dose (20 μ g injected in 4 lesions). This analysis is designed to be exploratory and will evaluate safety, clinical outcome and exploratory biomarkers to guide further clinical development. Clinical efficacy including ORR and DOR will be evaluated in relapsed or refractory FL patients who received ≥ 3 prior systemic therapies.

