## **5 Statistical Analysis**

### **5.1 Data Summaries and Conventions**

All data collected on case report forms will be provided in listings, except data collected only for confirmation of study entry criteria and for study administrative purposes. If any enrolled patient is found to not have valid documented informed consent, that patient's data will be excluded from the report, except as necessary to document the error.

Except where specified all continuous variables will be summarized with descriptive statistics (the number of non-missing values, mean, standard deviation, median, minimum and maximum) and all categorical variables will be summarized with frequency counts and percentages, by part, treatment, and overall.

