### **5.6.8 Immune Response and Biomarker Analyses**

All patients who have received at least one injection of G100 and have available immunohistochemistry (IHC), nanostring, or T cell receptor (TCR) data will be included in the biomarker analysis.

Anti-tumor cellular immunity (CD4, CD8 T cell, CD20, CD68, NKp46, FoxP3, CD8/CD4 ratio, CD8/FoxP3 ratio) by immunohistochemistry (IHC) will be explored. Post/pre treatment ratio will be summarized by treatment, and by subgroups of interest (irPR vs non-responder, pre-TLR4 $\geq$ 50% vs <50%, treatment naïve, relapsed/refractory patients, prior line of therapy 0-2 vs  $\geq$ 3). Post and pre treatment values will be compared using signed-rank test to identify significant changes post treatment. Association between clinical endpoints (irPR, irPR+MR, irPR+MR+SD, abscopal best % change better than -25%) and cellular immunity by immunohistochemistry will be explored using a logistic regression model for all dosed patients, and by treatment. Association between response (irPR) and pre-treatment TLR4 using different cutoffs will be presented in 2x2 tables and the proportion of response will be compared between TLR4 high and TLR4 low patients using Barnard's unconditional exact test. Comparison of post treatment change in immunohistochemistry will be explored between G100 monotherapy 10  $\mu$ g and G100 monotherapy 20  $\mu$ g patients.

Association between clinical response and nanostring genes (NK, M1 Markers, M2 Markers, and other genes of interest) using PBMC and tumor samples will be explored using a logistic regression model that includes  $\log_2$  transformed nanostring data. Post/pre mean expression ratio (as antilogarithm of the means of ( $\log_2$  post –  $\log_2$  pre)) for responder and non-responder, odds ratio, and nominal and adjusted p-values will be presented. Adjusted p-value is adjusted using False Discovery Rate (FDR) method. Ten most upregulated and ten most downregulated immune-related genes will be presented, with post/pre mean expression ratio and p-value from signed-rank test. Further, ten most highly differentially induced immune-related genes in clinical responders versus non-responders will be explored.

T cell receptor (TCR) clones not detectable at baseline in tumor/PBMC but become detectable or increased post-treatment in tumor/PBMC will be explored.

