## **7 Adjustment for Covariates**

In exploratory analyses comparing post treatment change in immunohistochemistry immune infiltrate between G100 monotherapy 10 µg and G100 monotherapy 20 µg patients, pre-treatment TLR4 and pre-treatment CD8/CD4 ratio are included as covariates in the analysis of variance model.

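### The IHC post/pre ratio is averaged untransformed, so its mean exceeds 1 when nothing has changed; the response scale of the 10 vs 20 microgram ANOVA is not stated

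*SAP*

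**What the plan says.** SAP 5.6.8 sets out three uses of the IHC data:

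- **Summary.** "Post/pre treatment ratio will be summarized by treatment, and by subgroups of interest", with no log scale or geometric mean mentioned. SAP 5.1 supplies the default: unless otherwise specified, "all continuous variables will be summarized with descriptive statistics (the number of non-missing values, mean, standard deviation, median, minimum and maximum".
- **Within-patient test.** "Post and pre treatment values will be compared using signed-rank test to identify significant changes post treatment".
- **Between-dose comparison.** "Comparison of post treatment change in immunohistochemistry will be explored between G100 monotherapy 10" and 20 microgram patients. SAP 7 adds that "pre-treatment TLR4 and pre-treatment CD8/CD4 ratio are included as covariates in the analysis of variance model". Neither section says whether the change being modelled is a raw ratio, a log ratio or a difference.

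For nanostring, the next paragraph of SAP 5.6.8 uses log2 data and defines the summary explicitly: "Post/pre mean expression ratio (as antilogarithm of the means of" log2 post minus log2 pre. That is a geometric mean ratio.

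SAP 8 says that p-values other than those for nanostring are nominal, in an exploratory early-phase study. No SD, effect size, alpha or power is given for any IHC analysis.

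**The concern.** A ratio is not symmetric about its no-change value. Doubling adds 1.0 to it and halving takes away only 0.5, so the arithmetic mean leans upward even when increases and decreases balance. The lean grows with the variance, so two groups with the same typical change but different noise would show different mean ratios. The planned responder and non-responder split could be affected in this way.

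Noise is likely here. The Protocol lets the baseline biopsy come from the target lesion or a non-target lesion (10.3.1), and lets the post-treatment biopsy move to another site if the treated tumor is unavailable (10.3.8). The two samples may therefore come from different lesions. Two of the listed markers, CD8/CD4 and CD8/FoxP3, are themselves ratios.

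A printed mean ratio above 1 could be read as immune infiltration when it is only scatter. The between-dose ANOVA raises a separate question. If its response were the raw ratio, the skewness would make the comparison inefficient.

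**Working it through.** The plan gives no figure to reproduce, so the check has two parts.

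**1. Mean ratio under no change.** Let r be the post/pre ratio and s the SD of its natural logarithm. The documents do not give s; 0.3 to 1.2 is assumed.

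If log r is symmetric about zero, r and 1/r are equally likely, and the average of such a pair, (r + 1/r)/2, is above 1 unless r = 1. For one doubling and one halving, (2 + 0.5)/2 = 1.25, while the geometric mean is √(2 × 0.5) = 1. So the direction of the shift needs only symmetry. Its size needs a distribution. For a lognormal ratio with median 1, the mean is exp(s²/2):

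| s | s²/2 | mean ratio | median and geometric mean |
|---|---|---|---|
| 0.3 | 0.045 | 1.05 | 1.00 |
| 0.5 | 0.125 | 1.13 | 1.00 |
| 0.7 | 0.245 | 1.28 | 1.00 |
| 0.8 | 0.320 | 1.38 | 1.00 |
| 1.0 | 0.500 | 1.65 | 1.00 |
| 1.2 | 0.720 | 2.05 | 1.00 |

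In samples of 15 patients with no true change, the sample mean ratio exceeds 1 in 70% (s = 0.3) to 95% (s = 1.2) of samples.

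**2. Between-dose ANOVA, if the response were the raw ratio.** The inputs were:

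- 10 microgram: 15. Protocol 14.2 says 18 patients "may receive intratumoral G100 alone following radiation therapy", 3 of them at 5 and 15 at 10 microgram.
- 20 microgram: 25. Protocol 14.2 says that in Part 3 "up to 25 patients will be enrolled and treated" at this dose. The optional Large Tumor group could add up to 4.
- These are enrolment figures; paired biopsies may be fewer.
- Assumed: s as above, true fold differences of 1.5 to 3.0, two-sided 0.05, and two covariates unrelated to outcome.

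Each setting was simulated 3,000 times, and the ANOVA was run on log r and on r from the same data. The simulation error of one power figure is at most √(0.5 × 0.5/3000), or 0.9 points. With 15 vs 25 patients and a 2-fold higher ratio at 20 microgram:

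| s | power, log ratio | power, raw ratio | loss (points) |
|---|---|---|---|
| 0.5 | 97.2% | 95.1% | 2.1 |
| 0.7 | 81.5% | 66.6% | 14.9 |
| 0.8 | 70.9% | 51.3% | 19.6 |
| 1.0 | 51.2% | 27.3% | 23.9 |
| 1.2 | 36.9% | 15.5% | 21.4 |

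Over all settings tried (8 vs 12 up to 15 vs 29 patients, fold differences 1.5 to 3.0), the loss ran from 0 to about 43 points. With no true difference, the raw-scale rejection rate was 3.1% to 5.5%, so type I error is not inflated.

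**The case against.** The strongest reply is that the plan already contains the safeguards. SAP 5.1 prints the median beside the mean, and the median ratio is 1 under the same null at every SD. Significant change is judged by a signed-rank test of post and pre values, which does not use the mean ratio. The analyses are exploratory with nominal p-values. All of this stands and lowers the priority. It does not correct a printed mean that has the wrong no-change value, and the signed-rank test does not cover the between-dose comparison.

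It can also be said that different assays may follow different conventions, and that the documents give no units or distribution for IHC. That is fair: the contrast with nanostring is not in itself an error, and the sizes above rest on an assumed lognormal. The direction needs only symmetry of the log-ratio.

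A log transform brings its own problem with zeros. For pre = 0 and post = 5, adding 0.01 gives log2(5.01/0.01) = 9.0, while adding 1 gives log2(6/1) = 2.6. In groups this small, one such patient could move the result. This objection stands and shapes the fix.

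Two stronger readings are tempting:

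- **That the ANOVA uses the raw ratio and loses a definite amount of power, say 10 to 20 points.** The SAP never says which scale is used, and the documents give neither the SD nor the effect size on which any loss depends.
- **That an inflated mean ratio drove the choice of 20 microgram.** Protocol 6.1 reports the increased CD8 infiltration as already observed when Part 4 was designed, and gives tolerability alongside it. Protocol 4.4.1 adds preclinical survival and sarcoma data. SAP 9 records that the sponsor terminated the study. Nothing shows that the tables planned in this SAP fed that decision.

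**Conclusion.** The point holds in a limited form. Followed as written, the SAP prints an arithmetic mean of raw IHC ratios. With symmetric log-ratios, its expected value under no change is above 1: between 1.13 and 2.05 for lognormal ratios with assumed SDs of 0.5 to 1.2. The geometric mean, already used for nanostring in the same section, has a no-change value of 1 at any SD and is the better summary.

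For the dose comparison, the defect is an unstated response scale, not a demonstrated loss of power. Any loss is conditional on the raw ratio being used and on the assumed SD, fold difference and group sizes. No false-positive problem arises on either scale. This is a cheap improvement of low priority.

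**What to change.** - **SAP 5.6.8:** report IHC change as the geometric mean post/pre ratio, the antilog of the mean of log2 post minus log2 pre, with a 95% CI. Keep the median.
- **Zeros:** pre-specify the constant added to zero values, tied to the smallest value the assay can report, and repeat the analysis once with another constant. Say how the rule applies to CD8/CD4 and CD8/FoxP3 when a denominator is zero.
- **SAP 7:** name log2(post/pre) as the response in the 10 vs 20 microgram ANOVA.

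The cost is a few sentences and a log transform in the analysis programs, with no new data. The one real downside is that the constant has to be chosen before the data are examined and its influence shown.

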## 5.6.2 Overall Response Rate (ORR) and Clinical Benefit Rate (CBR)

Overall response rate (ORR) using irRC will be defined as the number and percent of patients with best overall response of irCR or irPR. ORR with two-sided 95% Clopper-Pearson exact CI will be provided. Both unconfirmed and confirmed response using irRC criteria will be reported. The overall response using irRC is derived from time-point response assessments as follows:

- Immune-related complete response (irCR), complete disappearance of all lesions (whether measurable or not, and no new lesions), confirmed by a repeat, consecutive assessment no less than 4 weeks from first documentation
- Immune-related partial response (irPR), decrease in tumor burden  $\geq 50\%$  relative to baseline, confirmed by a consecutive assessment at least 4 weeks from first documentation
- Immune-related stable disease (irSD), not meeting criteria for irCR or irPR, in absence of irPD
- Immune-related progressive disease (irPD), increase in tumor burden  $\geq 25\%$  relative to nadir, confirmed by a repeat, consecutive assessment no less than 4 weeks from first documentation

In confirmed ORR summary, patients with best response of unconfirmed irPR will be summarized as irSD.

Overall response rate (ORR) using IWG will be defined as the number and percent of patients with best overall response of CR or PR.

Clinical benefit rate (CBR) will be defined as the number and percent of patients with best overall response of complete response, partial response or stable disease. CBR using both irRC and IWG will be reported.

In addition, abscopal tumor reduction will be summarized.

Lesion assessment (lesion type, organ site, evaluation method, diameter, and lesion status), as well as patient overall response based on both irRC and IWG criteria for lymphomas at each visit and the best overall response, will be presented in a data listing.

Overall tumor response using irRC criteria for all tumor lesions, irradiated sites, non-irradiated sites and abscopal sites, and overall tumor response using IWG criteria for all tumor lesions will be summarized. Overall tumor response for the following subgroups will also be provided:

- Relapsed/Refractory Patients
- Treatment Native Patients
- Patients with MR (minor response)
- Patients with MR (minor response) and Decrease in Abscopal Lesions
- Patients with PD at Study Entry
- Patients with Guided Injection of G100
- Patients with Not Guided Injection of G100

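### The IHC and TLR4 analyses in SAP 5.6.8 label response as irPR only, so any irCR patient would be misclassified, contrary to the irCR-or-irPR definition in SAP 5.6.2

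*SAP*

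**What the plan says.** SAP section 5.6.2 sets the response definition: "Overall response rate (ORR) using irRC will be defined as the number and percent of patients with best overall response of irCR or irPR". It lists irCR as a category of its own, "Immune-related complete response (irCR), complete disappearance of all lesions", separate from irPR. The clinical benefit rate in the same section also names complete response. Protocol section 14.3.3 defines ORR as CR plus PR.

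SAP section 5.6.8 uses different labels:

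- The IHC post/pre ratios are summarised by "subgroups of interest (irPR vs non-responder", followed by further subgroups.
- The logistic models cover "Association between clinical endpoints (irPR, irPR+MR, irPR+MR+SD, abscopal best % change better than -25%) and cellular immunity by immunohistochemistry".
- The TLR4 analysis, compared with Barnard's test, gives irPR in brackets as the meaning of response: "Association between response (irPR) and pre-treatment TLR4 using different cutoffs will be presented in 2x2 tables".
- The gene-expression analysis is worded "Association between clinical response and nanostring genes" and then contrasts responders with non-responders. It defines neither term.

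The abbreviation irCR does not occur in 5.6.8. The biomarker analysis set is "All patients who have received at least one injection of G100 and have available immunohistochemistry (IHC), nanostring, or T cell receptor (TCR) data", so patients with irCR are not excluded from it.

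**The concern.** Two sections of one SAP give different meanings to response. A programmer who follows 5.6.8 as written would code the event as best overall response equal to irPR. A patient with irCR would then sit with the non-responders, or in neither group if the labels are applied as strict subgroups. For the endpoint irPR+MR+SD, a complete responder would be a non-event alongside patients who progressed.

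What is at stake is the reading of the TLR4 and immune-infiltrate associations. TLR4-high patients are a named exploratory subgroup in Parts 4 and 5 (protocol section 6.1). Protocol section 9.6 hopes that the biomarkers will help stratify patients in later studies. With small groups, moving one or two of the best outcomes can change how such a table is read.

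**Working it through.** **1. The labels side by side**

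| Analysis in SAP 5.6.8 | Response label | irCR covered? |
|---|---|---|
| IHC post/pre ratio subgroup | irPR vs non-responder | No |
| IHC logistic endpoint 1 | irPR | No |
| IHC logistic endpoint 2 | irPR+MR | No |
| IHC logistic endpoint 3 | irPR+MR+SD | No |
| IHC logistic endpoint 4 | Abscopal best change better than -25% | Not label-based, so unaffected |
| TLR4 2x2 tables, Barnard's test | irPR | No |
| Nanostring | Clinical response, responder | Undefined |

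The MR category cannot absorb a complete responder, because SAP section 5.6.2 caps it below a 50% decrease. Neither document says that irPR means irPR or better. SAP section 9, which lists changes from the protocol's planned analyses, mentions no narrower responder definition.

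**2. Does the plan expect complete responses?**

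This uses the Part 5 inputs in SAP section 3.4: n = 20, a signal at 5 or more CRs, and CR rates of 10% (historical), 32% (assumed) and 40% (target). The plan's figures reproduce with the exact binomial distribution:

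- P(X ≥ 5 | 20, 0.32) = 0.817; the plan states 82% power.
- P(X ≥ 5 | 20, 0.10) = 0.043, within the stated one-sided 0.05.
- P(X ≤ 4 | 20, 0.40) = 0.051; the plan states 5.1%.

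The expected number of CRs is 20 × 0.10 = 2.0, 20 × 0.32 = 6.4 and 20 × 0.40 = 8.0. Even at 10%, the chance of at least one CR is 1 − 0.90^20 = 0.878. The planning assumptions therefore do not treat CR as an empty category. They say nothing about how many irCRs occurred.

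**3. Size and direction, with assumed counts**

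The documents give no irCR counts. Assume 10 TLR4-high and 10 TLR4-low patients, with 7 and 2 responders when irCR and irPR both count. The p-values are two-sided, from Barnard's unconditional exact test, the method that 5.6.8 names.

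| Assumed irCRs | Handling | High vs low | Difference | p |
|---|---|---|---|---|
| None, or irCR counted as response | – | 7/10 vs 2/10 | 70% − 20% = 50 points | 0.041 |
| 1 in high group | Non-responder | 6/10 vs 2/10 | 60% − 20% = 40 | 0.095 |
| 2 in high group | Non-responder | 5/10 vs 2/10 | 50% − 20% = 30 | 0.22 |
| 2 in high group | Left out | 5/8 vs 2/10 | 62.5% − 20% = 42.5 | 0.098 |
| 1 in low group | Non-responder | 7/10 vs 1/10 | 70% − 10% = 60 | 0.008 |
| 2 in low group | Non-responder | 7/10 vs 0/10 | 70% − 0% = 70 | 0.0009 |
| 2 in low group | Left out | 7/10 vs 0/8 | 70% − 0% = 70 | 0.002 |

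In this example irCRs in the high group shrink the association and irCRs in the low group inflate it.

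**The case against.** The best reply is that irPR is shorthand for irPR or better. The series irPR, irPR+MR, irPR+MR+SD looks like a ladder of cut-points. A complete responder also exceeds the 50% decrease that defines irPR. And "irPR vs non-responder" is set against a term that, under 5.6.2, cannot include irCR. This reading is possible, but it is stated nowhere. It is weakened by the third endpoint, which lists its categories one by one and still omits the complete response that the matching clinical benefit rate names.

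A second reply is that no irCR may have occurred. SAP section 9 refers to study termination, so the SAP was finalised late. Section 5.6.2 gives a downgrade rule for unconfirmed irPR and none for unconfirmed irCR. That fits irPR being the best category seen, but does not show it. If it is so, no result changes.

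A third reply is that the consequence is small, and this stands. Protocol section 14.3.2 presents the associations as exploratory. SAP section 8 gives nominal p-values apart from the FDR-adjusted nanostring results. No sample size, error rate or decision rule depends on 5.6.8. ORR and CBR are defined correctly, and the planned listings show each patient's best overall response, so an irCR would be visible there.

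**Conclusion.** The inconsistency is real and should be corrected. It covers the IHC subgroup comparison, the three category-based logistic endpoints and the TLR4 tables. For nanostring the fault is a missing definition. The actual effect cannot be sized from the documents: it is nil with no irCRs, and the illustration above rests on assumed counts.

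Three stronger conclusions that a reader might draw are not supported:

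- **That every biomarker endpoint misplaces complete responders.** The abscopal endpoint rests on percent change, and nanostring does not use the irPR label.
- **That the associations are always pulled toward the null.** The direction depends on which marker group holds the irCRs.
- **That Part 5 is where the harm mainly falls.** The Part 5 signal rule counts CRs directly and does not use 5.6.8. The Part 5 figures above show only that complete responses were anticipated in planning.

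**What to change.** Define responder once at the start of SAP section 5.6.8 as best overall response of irCR or irPR by irRC, in line with 5.6.2. Then:

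- Use irCR+irPR, irCR+irPR+MR and irCR+irPR+MR+SD as the three category-based logistic endpoints.
- Apply the same responder definition to the IHC subgroup comparison, the TLR4 tables and the nanostring analyses.
- State whether confirmed or unconfirmed response is used, since 5.6.2 reports both and 5.6.8 does not choose.

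Leave the abscopal percent-change endpoint as it is. The cost is a few lines of SAP text and the matching derivation in the analysis dataset specification. No new data are needed, and sample size, power and alpha are untouched. If the tables have already been run, check the best-response listing for irCR: if there is none, adding irCR changes no result in the irPR-labelled analyses.

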## **5.7 Safety Evaluation**

Safety evaluation will be based on safety population.

